7.1 Inclusion Criteria

Subject eligibility is determined according to the following criteria prior to entry into the study:

1. In the opinion of the investigator, the subject is capable of understanding and complying with protocol requirements.
2. The subject signs and dates a written, informed consent form and any required privacy authorization prior to the initiation of any study procedures.
3. The subject is a healthy male or female aged 18 to 40 years, inclusive.
4. The subject has been in a steady relationship for ≥ 3 months and plans to remain in that relationship for the duration of the study, and is currently sexually active (≥ 2 times per week).
Note: Partners are not allowed to enroll in this trial.
5. The subject has a body mass index (BMI) of 18 to 35 kg/m^2 , inclusive, at the Screening and Baseline Visits.
6. If female, the subject has a regular menstrual cycle (note: amenorrhea resulting from hormonal contraceptives is not exclusionary).
7. A female subject of childbearing potential* who is sexually active with a nonsterilized* male partner agrees to routinely use adequate contraception* from signing of informed consent throughout the duration of the study and for 30 days after the last dose.

*Definitions and acceptable methods of contraception are defined in Section [9.1.13](#) and reporting responsibilities are defined in Section [9.1.14](#).

8. The subject has normal sexual functioning, as defined by a CSFQ-14 total score >47 (men) or >41 (women) at the Screening and Baseline Visits.
9. If female, the subject taking allowed hormonal contraceptives is on a stable dose for ≥ 3 months prior to the Baseline Visit and continues on the stable dose for the duration of the study.

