6.0 DETERMINATION OF SAMPLE SIZE

Approximately 352 male and female subjects will be randomized to 4 treatment arms. Randomization will be stratified by sex. Men and women will be enrolled in approximately equal proportions (ie, 50% men and 50% women overall).

Assuming an SD of 8.5 for the change from Baseline in CSFQ-14 total score, a total of 352 male and female subjects (88 subjects per arm) is sufficient to achieve $\geq 80\%$ power to detect a difference of 4.0 for vortioxetine 20 mg vs paroxetine 20 mg or for vortioxetine 10 mg vs paroxetine 20 mg by a 2-sample t-test with a 0.025 2-sided significance level. Given the proposed Holm-Bonferroni method (see Section 7.9.3) for multiplicity control, the power to achieve the significance for each vortioxetine dose is approximately 85%.

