7.1.3 Definition of Study Day and Study Visit Windows

A windowing convention will be used to determine the analysis value for a given study visit that applies to observed data.

Study Day -1 corresponds to the date of the Baseline visit, ie, the randomization date. Other study days are defined relative to Study Day 1, the date of first double-blind study drug dose. Relative day is calculated as (date of interest – date of first dose +1) for study days on or after the

date of first dose and as (date of interest – date of first dose) for study days prior to the first dose date.

For each visit, a window will be defined such that the lower and upper bounds of each window is generally the midpoint between 2 consecutive study visits. The visit windows and applicable study day ranges are presented below in [Table 7.a](#).

Table 7.a Visit Windows

Nominal Visit Week	Nominal Visit Day	CSFQ-14, PGI-I, C-SSRS	Vital signs	Lab, PE,Weight,	PK
Baseline	-1 (a)	≤1 (b)	≤1	≤1	≤1 (b)
1	7	2 – 10			
2	14	11 – 17	2-24		
3	21	18 – 24			2-24
4	28	25 – 31			25-31
5	35	≥32	≥25	≥2	≥32
7	49				

(a) Baseline day has been defined as Day -1 in keeping with Clinical Data Interchange Consortium standards. There is no Day 0.

(b) No baseline assessment for PGI-I or pharmacokinetic (PK) sampling.

More than 1 result for a parameter may be obtained in a visit window. In such an event, the result with the date closest to the scheduled visit day will be used. In the event of 2 observations equidistant to the scheduled visit day, the later of the observations will be used. Treatment Period Last Visit values will be defined irrespective of falling in a particular window. Hence, the windowed Week 8 value may be different than the Last Visit value.

In general, the baseline value for a variable is defined as the last observation prior to the first dose of double-blind study medication (visit date \leq first dose date), including the screening value, if necessary.

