7.9.3 Primary Efficacy Endpoint(s)

Mean change from Baseline in the CSFQ-14 total score difference for vortioxetine vs paroxetine after 5 weeks of treatment will be the primary endpoint. The primary analysis will be based on analysis of covariance (ANCOVA) using the last observation carried forward (LOCF) technique, with treatment, center, and sex as fixed factors, and baseline CSFQ-14 total score as covariate. The comparisons will be between each vortioxetine dose (10 or 20 mg) and paroxetine, and both statistical tests will be 2-sided.

The following example SAS code will be used for the ANCOVA analysis:

```
Proc mixed data=all;
  - class treat center sex;
  - model Change= Baseline treat center sex;
  - lsmeans treat;
```

In the above model, Baseline is the baseline value and Change is the change from baseline value.

The Holm-Bonferroni method will be used to adjust for multiplicity and control the familywise type I error rate at a significance level of 0.05. If the smaller of the 2 P-values is <0.025 , significance is obtained for the associated vortioxetine dose and the other dose will then be evaluated at a 0.05 significance level. Although vortioxetine will be compared with paroxetine in the primary analysis, paroxetine will also be compared with placebo to validate the study. The primary analyses will also be repeated based on the PPS if more than 5% of the total subjects in the FAS have major protocol violations.

As supportive analyses, the sex-by-treatment interaction term will be added to the primary analysis model to further check the sex effect on the treatment. The similar ANCOVA analyses will also be performed using the observed case (OC) data.

Change from Baseline in the CSFQ-14 total score will also be analyzed based on a mixed model for repeated measurements (MMRM) with treatment, center, week, treatment-by-week interaction and sex, as fixed effects, and baseline CSFQ-14 total score, and CSFQ-14 total score-by-week as covariates. The effect at each time point for each treatment is allowed to vary freely and an unstructured covariance matrix is assumed.

The SAS code for the MMRM analysis will be as follows:

```
Proc mixed data=all;
  - class week treat center subject;
  - model Change = baseline*week baseline treat center week week*treat sex /solution;
  - repeated week/subject=subject type=UN;
  - lsmeans week*treat / cl pdiff.
```

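### CSFQ-14 is scored at both Screening and Baseline, but the primary ANCOVA and the MMRM adjust only for Baseline: a valid analysis that forgoes a possible gain in precision

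*SAP*

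**What the plan says.** Protocol 7.1, criterion 8, states: "The subject has normal sexual functioning, as defined by a CSFQ-14 total score >47 (men) or >41 (women) at the Screening and Baseline Visits". The schedule of procedures (Appendix A of both documents) places the CSFQ-14 at Screening, at Baseline and at each weekly visit. The Screening Period lasts up to 4 weeks.

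SAP 7.9.3 and Protocol 13.1.3.1 specify the same primary ANCOVA on change from Baseline with LOCF, "with treatment, center, and sex as fixed factors, and baseline CSFQ-14 total score as covariate". The supportive MMRM in SAP 7.9.3 uses the Baseline score and a Baseline-by-week term. SAP 7.9.4 and Protocol 13.1.3.2 apply the same single-score adjustment to the total score at each visit, and analyze the subscales in the same manner; the SAP adds individual items.

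Under SAP 7.1.3, "the baseline value for a variable is defined as the last observation prior to the first dose of double-blind study medication", with the Screening value used if needed. That fallback is the only use of the Screening score in the efficacy models. SAP 7.9.3 names further covariates to explore (sex, pooled center, race, weight, BMI, age). Screening CSFQ-14 is not among them, although the list is not worded as closed. No reason is given for leaving it out.

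**The concern.** A pre-randomization measurement of the outcome is usually among the best covariates available, and here there are two. If the Screening score predicts Week 5 beyond what Baseline already predicts, omitting it leaves removable between-subject variance in the residual. That variance enters the standard errors of both vortioxetine-paroxetine contrasts, of the paroxetine-placebo contrast meant to validate the study, and of the male and female subgroup analyses, which have roughly 44 per arm. Because the score precedes randomization, adjusting for it introduces no bias in these contrasts and leaves the endpoint unchanged. What is at stake is precision only.

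**Working it through.** **1. The plan's own power.** Inputs from SAP 6.0:

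- Spread: "Assuming an SD of 8.5 for the change from Baseline in CSFQ-14 total score".
- Size: 88 per arm, 352 in all.
- Effect: "power to detect a difference of 4.0 for vortioxetine 20 mg vs paroxetine 20 mg", and the same size of effect for the 10 mg dose.
- Test: each dose is compared "by a 2-sample t-test with a 0.025 2-sided significance level".

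From these:

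- SE of a contrast = 8.5 × √(2/88) = 1.281, and 4.0/1.281 = 3.12.
- Power = Φ(3.12 − 2.24) = 81.1% by the normal approximation, or 80.4% by noncentral t. The plan says at least 80%.
- Holm power per dose, by simulation with a shared paroxetine arm and a true difference of 4.0 for both doses, is 85.5%. The plan says about 85%.

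Both figures reproduce. They rest on an unadjusted t-test, so neither depends on any covariate.

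**2. Formula for the gain.** Let a = Screening-Baseline, b = Baseline-Week 5 and c = Screening-Week 5 be within-arm correlations. The proportional fall in residual variance from adding Screening to a model that already has Baseline is the squared partial correlation:

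fall = (c − ab)² / [(1 − a²)(1 − b²)]

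If all three equal r, this reduces to [r/(1 + r)]². If c = ab, so that Screening relates to Week 5 only through Baseline, it is zero. Taking change or the Week 5 score as the response makes no difference once Baseline is in the model.

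**3. Numbers.** The documents give no correlations, so every row is an assumption. The equivalent n is 88/(1 − fall).

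| a / b / c | Fall in residual variance | SE smaller by | Equivalent n per arm |
|---|---|---|---|
| 0.7 / 0.6 / 0.42 | 0% | 0% | 88 |
| 0.7 / 0.5 / 0.4 | 0.7% | 0.3% | 89 |
| 0.7 / 0.6 / 0.5 | 2.0% | 1.0% | 90 |
| 0.6 / 0.6 / 0.5 | 4.8% | 2.4% | 92 |
| 0.4 / 0.4 / 0.4 | 8.2% | 4.2% | 96 |
| 0.5 / 0.5 / 0.5 | 11.1% | 5.7% | 99 |
| 0.6 / 0.6 / 0.6 | 14.1% | 7.3% | 102 |
| 0.7 / 0.7 / 0.7 | 17.0% | 8.9% | 106 |

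Example, third row: (0.5 − 0.42)²/(0.51 × 0.64) = 0.0064/0.3264 = 0.020.

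**4. Effect on power at b = 0.6.** Assume equal variances at Baseline and Week 5. The score SD is then 8.5/√(2 × 0.4) = 9.50, and the residual SD with Baseline only is 9.50 × √0.64 = 7.60. Power at two-sided 0.025 (normal approximation) is 89.4%. Adding Screening gives:

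- a = 0.7, c = 0.42: residual SD 7.60, power 89.4%.
- a = 0.7, c = 0.5: residual SD 7.53, power 90.0%.
- a = 0.6, c = 0.5: residual SD 7.42, power 90.9%.
- a = 0.6, c = 0.6: residual SD 7.05, power 93.6%.

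**5. Selection.** Criterion 8 cuts off both scores from below. As an illustration, take unselected correlations and an assumed cut at the 20th percentile of each score. By simulation the fall then drops from 14% to about 11% (0.6/0.6/0.6), from 4.8% to 3.5% (0.6/0.6/0.5) and from 2.0% to 1.5% (0.7/0.6/0.5).

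**The case against.** The strongest reply is that nothing is broken. ANCOVA on one pre-treatment score is valid, Protocol and SAP agree on it, and the sample size reproduces without it. At an assumed Baseline-Week 5 correlation of 0.6 the planned model already has about 89% power for a single contrast at 0.025. All of that stands.

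The reply continues that the gain may be negligible. Screening and Baseline are both off drug and at most 4 weeks apart, whereas Week 5 follows treatment that is active in three of the four arms. A Screening-Baseline correlation above the other two is therefore at least as plausible as equality, and that pattern gives gains near 0 to 2%. This also stands, and the low end belongs in any stated range. In the other direction, entry selects healthy adults in steady relationships. That favors a stable personal level plus visit-to-visit variation, the structure under which equal correlations arise. The documents cannot settle which applies.

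A reader might infer three stronger things that the documents do not support:

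- That the Screening score is thrown away. It decides eligibility and is the fallback baseline.
- That a single CSFQ-14 score is too noisy to serve as the baseline. No reliability figure is given, and Protocol 6.2.3 describes the instrument as validated. Truncation at the entry cut-off does not single out Baseline either, since Screening is truncated in the same way.
- That adding Screening is bound to narrow the confidence intervals. If it carries nothing beyond Baseline, no narrowing is expected.

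**Conclusion.** The concern holds as a missed efficiency. Two pre-treatment scores are collected, and only one enters the ANCOVA and the MMRM. The planned analysis is not biased, its type I error is not in question, and the stated power does not rest on this choice. A reading that the primary analysis is flawed or the trial underpowered because of it would be wrong.

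The gain cannot be fixed from the documents. Over the correlations considered it runs from 0% to about 17% of residual variance, with about 2% at 0.7/0.6/0.5. The upper figure needs all three correlations at 0.7. The calculation also sets aside sex and center, so the relevant correlations are those remaining after adjustment for them. The change is worth making because it costs almost nothing and uses data already collected, not because a particular gain is assured.

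**What to change.** Before unblinding, amend SAP 7.9.3 and 7.9.4 and Protocol 13.1.3.1 and 13.1.3.2 as follows:

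- **Total-score ANCOVA:** add the Screening CSFQ-14 total score as a second continuous covariate, `model Change = Baseline Screening treat center sex`. Keep change from Baseline as the response so that the endpoint is unchanged.
- **MMRM:** add both Screening and Screening-by-week, parallel to the existing Baseline terms.
- **Subscales and individual items:** use the matching Screening subscale or item score, not the total.
- **Missing Baseline score:** where Screening substitutes for it, both covariates take the same value.

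The cost is one degree of freedom in the ANCOVA and five in the MMRM (one for Screening and four for its interaction with five weekly visits). It needs no new data or visits, only a wording change in each document. The downside is that there may be no gain. Timing matters: Protocol 13.1 has the SAP finalized before unblinding, and the same term added afterwards could look data-driven.

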7.9.4 Secondary Efficacy Endpoints

Change from Baseline in CSFQ-14 total score for vortioxetine (10mg and 20mg separately) vs paroxetine, paroxetine vs placebo, and vortioxetine vs placebo at each visit will also be analyzed using ANCOVA and LOCF, with treatment, center, and sex as fixed factors, and baseline CSFQ-14 total score as covariate. MMRM method will also be used in sensitivity analyses. Similar analyses will also be performed for the male and female subgroups. Comparisons to placebo will be made at the significance level of 0.05 outside of multiplicity control.

The percentage of subjects meeting criteria for sexual dysfunction (ie, CSFQ-14 total score \leq 47 for men and \leq 41 for women) at any visit (using both LOCF and OC) during the double-blind Treatment Period will be analyzed by logistic regression, adjusting for baseline CSFQ-14 total score, sex, and treatment.

The following SAS code will be used for the logistic regression analysis:

```
Proc logistic data=all descending;
  - class treat;
  - model resp = treat baseline sex;
```

In the above model, Baseline is the baseline value for the corresponding response variable.

In addition, the sex effect on sexual dysfunction will also be investigated by the inclusion of the sex-treatment interaction term and the sex subgroup analysis.

Change from Baseline in CSFQ-14 subscales 5 dimensions, 3 phases, and individual items of the sexual response cycle will be analyzed at all visits using ANCOVA (LOCF) and MMRM similar to the primary analysis.

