13.1.3.2 Secondary Analyses

Change from Baseline in CSFQ-14 total score for vortioxetine vs paroxetine, paroxetine vs placebo, and vortioxetine vs placebo at each visit will also be analyzed using ANCOVA and LOCF, with treatment, center, and sex as fixed factors, and baseline CSFQ-14 total score as covariate. Similar analyses will also be performed for the male and female subgroups. Comparisons to placebo will be made at the significance level of 0.05 outside of multiplicity control.

The percentage of subjects meeting criteria for sexual dysfunction (ie, CSFQ-14 total score ≤ 47 for men and ≤ 41 for women) at any visit (using LOCF) during the double-blind Treatment Period will be analyzed by logistic regression, adjusting for baseline CSFQ-14 total score, sex, and treatment.

Change from Baseline in CSFQ-14 subscales 5 dimensions and 3 phases of the sexual response cycle will be analyzed at all visits using ANCOVA and LOCF similar to the primary analysis.

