7.9.5 Additional Endpoints

The percentage of subjects meeting criteria for sexual dysfunction (ie, CSFQ-14 total score ≤ 47 for men and ≤ 41 for women) at any 2 consecutive visits (using LOCF) during the treatment period will be analyzed by logistic regression, adjusting for baseline CSFQ-14 total score, sex, and treatment.

Time to sexual dysfunction as assessed by the CSFQ-14 and time to CSFQ-14 negative response (defined as the decrease from Baseline in CSFQ-14 total score ≥ 3) will be analyzed using a Cox model with an exact method to handle ties, with treatment and sex as factors. The SAS code for the time-to-event analysis will be as follows:

```
proc phreg;
  class treat;
  model T_Sexdys*status_1(0) = treat sex/ ties=exact;
```

The analysis will also be supplemented with plots of Kaplan-Meier estimates of sexual dysfunction.

CSFQ-14 shift from normal (ie, CSFQ-14 total score > 47 for men and > 41 for women) at Baseline to abnormal (ie, CSFQ-14 total score ≤ 47 for men and ≤ 41 for women), and CSFQ-14 negative responders (decrease from Baseline in CSFQ-14 total score ≥ 3) will be analyzed at all visits by logistic regression, adjusting for baseline CSFQ-14 total score, sex, and treatment.

PGI-I will be analyzed by study visit using ANCOVA and LOCF, with treatment, center, and sex as fixed factors. MMRM analysis will also be performed.

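### SAP 7.9.4: the note under the logistic code defines Baseline as the baseline of a response that is constant at entry, contradicting the planned adjustment for baseline CSFQ-14 total score; the code also names no reference arm or contrast

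*SAP*

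**What the plan says.** For dysfunction at any visit, SAP 7.9.4 states that the percentage "will be analyzed by logistic regression, adjusting for baseline CSFQ-14 total score, sex, and treatment". Protocol 13.1.3.2 names the same terms: "adjusting for baseline CSFQ-14 total score, sex, and treatment". The SAP then commits to specific code: "The following SAS code will be used for the logistic regression analysis". The procedure line is "Proc logistic data=all descending", treatment is the only class variable, and the model is "model resp = treat baseline sex". No reference level, parameterisation, contrast, least-squares-means or odds-ratio statement follows. The note beneath reads: "In the above model, Baseline is the baseline value for the corresponding response variable".

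SAP Table 7.b classes dysfunction as a binary variable (total score at or below 47 for men, 41 for women). Protocol 7.1, criterion 8, fixes its value at entry: "The subject has normal sexual functioning, as defined by a CSFQ-14 total score" above those same cut-offs, at both Screening and Baseline.

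SAP 7.9.5 plans the same regression for dysfunction at two consecutive visits, the shift to abnormal, and negative response. Of the last two it says that they "will be analyzed at all visits by logistic regression, adjusting for baseline CSFQ-14 total score, sex, and treatment". It gives no separate logistic code for any of the three.

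**The concern.** Two things in one short block do not fit the rest of the plan.

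**The covariate.** The note ties Baseline to the response variable in the model. That response is dysfunction status, which is the same for every eligible subject at Baseline. A programmer who follows the note would adjust for nothing; one who follows the sentence above the code would adjust for the total score. The literal reading is not far-fetched, because SAP 7.5 lists sexual dysfunction status among the baseline characteristics, so a variable matching the note may well exist.

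**The comparison.** The secondary objectives (SAP 4.2) are pairwise: each vortioxetine dose against paroxetine, paroxetine against placebo, and each vortioxetine dose against placebo. Neither the logistic text nor the code names a pair. What the output shows is then settled by data coding and software defaults, possibly after unblinding.

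At stake is the interpretation of one named secondary endpoint and three additional endpoints.

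**Working it through.** **Plan's own figures.** The plan states no power or sample size for the logistic analysis. The figures it does give are for the primary analysis. With 88 per arm, difference 4.0, SD 8.5 and two-sided 0.025, the noncentral-t power is 0.804 (stated: at least 80%). Simulating the Holm procedure with a shared paroxetine arm gives 0.855 per dose (stated: about 85%). Both reproduce, and neither depends on the logistic code.

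**Step 1: the literal covariate.** Under criterion 8, baseline dysfunction status is 0 for all eligible subjects. The design matrix has 6 columns (intercept, three treatment terms, Baseline, sex) and rank 5. The Baseline coefficient is not estimable, and the model reduces to treatment plus sex. The same holds for the other binary endpoints: the shift and the two-visit criterion use the same cut-offs, and a negative response is a fall of at least 3 from Baseline, which is 0 at Baseline by definition. The total score itself varies above the cut-off and is estimable.

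**Step 2: cost of losing the total score (illustration).** Assumed: 88 per arm; half men; baseline = cut-off + 1 + |N(6, 5)| rounded; mean changes of -1, -2, -2.5 and -5 for placebo, 10 mg, 20 mg and paroxetine; SD 8.5; one post-baseline score. In one simulated data set the odds ratio against paroxetine moved from 0.31 to 0.36 (10 mg) and from 0.63 to 0.73 (20 mg) when the total score was omitted. Over 600 simulated trials, power for 20 mg against paroxetine was 0.29 with it and 0.27 without. These values show direction only.

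**Step 3: which odds ratios are printed.** By default PROC LOGISTIC takes the last sorted level as reference (general software knowledge, not from the documents). The documents do not fix the coding of the treatment variable.

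| Arm order | Last level | Vortioxetine-paroxetine odds ratios printed |
|---|---|---|
| Letters A-D, Protocol Table 8.a | Paroxetine | Both |
| Order of listing, SAP 7.1.2 | Placebo | Neither |
| Alphabetical labels | Vortioxetine 20 mg | 20 mg only, inverted |

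One reference arm among four gives three pairs. The objectives imply five, so no default table shows them all.

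**Step 4: what the per-arm p-values test.** The default class coding is effect coding (again software knowledge). With arm log-odds l and variance v = 1/[n p(1 - p)], ignoring sex and baseline:

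- pairwise: l_j - l_par, SE = sqrt(v_j + v_par)
- effect-coded: l_j - mean of the four l, SE = sqrt[(9/16) v_j + (1/16) × sum of the other three v]

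Worked case, 20 mg, assumed rates 25/30/50/20% (10 mg, 20 mg, paroxetine, placebo):

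- l = -1.099, -0.847, 0, -1.386; mean -0.833; v = 0.0606, 0.0541, 0.0455, 0.0710.
- Pairwise: -0.847, SE sqrt(0.0541 + 0.0455) = 0.316, p = 0.007, odds ratio 0.43.
- Effect-coded: -0.847 + 0.833 = -0.014, SE sqrt(0.0304 + 0.0111) = 0.204, p = 0.94.

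| Assumed rates, % (10 mg / 20 mg / paroxetine / placebo) | 10 mg: pairwise p; effect-coded p | 20 mg: pairwise p; effect-coded p |
|---|---|---|
| 25 / 30 / 50 / 20 | 0.0007; 0.21 | 0.007; 0.94 |
| 20 / 25 / 50 / 20 | 0.00005; 0.06 | 0.0007; 0.54 |
| 20 / 20 / 50 / 30 | 0.00005; 0.03 | 0.00005; 0.03 |

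The 0.94 is close to the worst case: the four assumed log-odds average to 30.3% on the probability scale, almost exactly the 30% assumed for 20 mg.

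**Step 5: is the fit itself wrong?** No. In the data set of Step 2, fitted with the total score, 10 mg against paroxetine gave p = 0.003 under all three arm orders, while the printed effect-coded p was 0.049. The contrast is in the model; it has only to be requested.

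**The case against.** The best defence has three parts.

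**The covariate is named correctly everywhere else.** The sentence above the code, SAP 7.9.5 and Protocol 13.1.3.2 and 13.1.3.3 all name baseline CSFQ-14 total score. The note can be read as the baseline of the underlying score, and a constant covariate would be noticed at the first run. This stands, to the extent that a reader who infers that the planned adjustment has been dropped goes beyond the documents: that follows only if the note overrides all the other text. It does not remove the contradiction, because the note belongs to code stated as what will be used.

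**The comparison is not lost.** A reader might infer that the code yields no vortioxetine-paroxetine test. The documents do not support that. Under the protocol's treatment letters both odds ratios print with confidence intervals, and under any coding the contrast can be recovered. What stands is that the result depends on an unstated coding choice.

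**SAP code blocks are skeletons.** The primary ANCOVA block also stops short of a pairwise request. This largely stands, so the missing contrast is the lesser half of the point. Two differences remain: the ANCOVA block is labelled an example and its text names the comparisons, whereas the logistic block has neither feature. The MMRM block does request pairwise differences. It is also fair that the five pairs are not listed for this endpoint; they come from the objectives and from the paragraph on change in total score.

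**Conclusion.** The point holds as an internal contradiction plus an under-specified output. The note in SAP 7.9.4, read literally, makes the baseline covariate a constant that cannot be estimated, against the adjustment that the same section and the protocol require. The code leaves the reference arm to sort order, and its default per-arm p-values do not test any planned pair.

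The consequence is small. Only the secondary dysfunction endpoint and the additional binary endpoints are touched, and SAP 7.1.2 places them outside multiplicity adjustment. The primary ANCOVA, the Holm test and the sample size do not change. In the simulation, losing the covariate moved power from 0.29 to 0.27. If per-arm p-values were mistaken for pairwise ones, the reported figure could lie anywhere from 0.03 to 0.94 where the pairwise value is 0.007 or less.

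This rests on assumed dysfunction rates, baseline distribution and arm effects, on PROC LOGISTIC defaults known from general use, and on all subjects meeting criterion 8. An entry violation could give a few non-zero baseline values.

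**What to change.** In SAP 7.9.4, replace the note by: *Baseline is the baseline CSFQ-14 total score for all binary endpoints.*

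In the same edit, name the reference arm and list the odds ratios to be reported with confidence intervals and p-values: each vortioxetine dose against paroxetine, paroxetine against placebo, and each vortioxetine dose against placebo. One way to write it, with the arm label adapted to the data set:

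`class treat(ref='Paroxetine 20 mg') sex / param=glm; model resp(event='1') = treat base_csfq_total sex; lsmeans treat / diff oddsratio cl;`

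State in SAP 7.9.5 that its logistic analyses use the same specification.

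The cost is a few lines of SAP text before unblinding and programming. No new data, design change or recalculation is needed.
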